Introduction: The Scientific Premise of this study is that the high level of obesity displayed by African American (AA) women is due to their ability to secrete large amounts of insulin when high glycemic index foods are consumed.

Mechanisms: When AA women eat a diet rich in starchy or sugary food (a “high-glycemic” diet that stimulates insulin secretion), the food that is eaten is stored as fat rather than being burned as fuel.

Existing knowledge: AA women, as a group, are more obese than AA men or Caucasians of either sex. We believe that this is due to the unique biology of AA women. Specifically, AA women secrete a lot of insulin when they eat sugary foods. Because insulin promotes fat storage, this could make the food unavailable to burn as fuel and explain greater body fat in AA women. In fact, AA women have lower energy requirements than white women, and are more energetically efficient. High insulin secretion, however, is only one factor that determines insulin action; another major factor is insulin sensitivity. Our data have shown that over time, weight (fat) gain in obesity-prone AA women is higher in those who are more insulin sensitive, whereas “obesity-resistant” AA women have lower insulin sensitivity. Our data also suggest that the fat-storing actions of insulin in AA women are worsened by a diet that promotes insulin secretion. This diet is called a “high-glycemic diet.” Finally, our data have shown that over time weight (fat) gain in AA women is predicted by the combination of insulin sensitivity and the amount of sugar and starch in the diet (called diet “glycemic load”).

Need for a trial: We think that AA women will have an easier time losing weight if they eat a “low glycemic” diet. In fact, we have seen in our research that AA women lose 50% more fat with low- vs high-glycemic diet. This project will test this in a larger group of women, under controlled conditions. We will also see if it is easier to keep the weight off with a low glycemic

diet. Additionally, we will determine if insulin sensitivity affects the weight loss response to diet composition. This study will test the effect of high and low glycemic diets for weight loss and weight-loss-maintenance in obese AA women.

6b Background and rationale: choice of comparators

Explanation for choice of comparators:

We will be comparing a low glycemic diet versus a high glycemic diet. These diets were chosen based on our previous research mentioned above.

7. Objectives

Specific objectives or hypotheses

1.1 Research hypothesis

AA women with lower SI and/or higher AIRg will lose more FM when on low-CHO, versus low-fat diet, and that this effect would be modulated by differences in EE (REE, TEE or ME).

2. Study objectives

To examine the independent and interactive effects of SI, AIRg, and diet with changes in fat mass (FM), resting (REE) and total energy expenditure (TEE), and mechanical efficiency (ME) in AA women with obesity during weight loss.

2.1 Primary objective

To examine the independent and interactive effects of SI, AIRg, and diet on changes in fat mass in African American women with obesity.

2.2 Secondary objectives

To characterize REE, TEE, and ME following low-CHO, versus low-fat diet.

8. Trial design

The CHAMPION study was designed as a two-arm randomized clinical trial. Randomization (1:1) was performed using a computer-generated randomization scheme prepared with PROC PLAN in SAS Ver. 9.4.

Methods: Participants, interventions, and outcomes

9. Study setting

Data will be collected from healthy, but obese, AA women in the Birmingham, AL, metro area in The United States of America. Study testing will be performed in the Core facilities of the Center for Clinical and Translational Science (CCTS), Nutrition Obesity Research Center (NORC), and Diabetes Research Center (DRC) at UAB.

10. Eligibility criteria:

Participants will provide written, informed consent before the start of the study (see Appendix 1 for sample Informed Consent Form).

Inclusion criteria

Participants eligible for the study must comply with all of the following at randomization:

1. Age 19-65 years
2. African American female
3. BMI 30-45 kg/m²
4. Sedentary to moderately active
5. Normal menstrual cycle in premenopausal women
6. Normal glucose tolerance based on HbA1c less than 6.0%

Exclusion criteria

1. History of eating disorder
2. Daily use of tobacco (>1 pk/wk)
3. Change in weight greater than 5 lb in the previous 3 months
4. Presence of any condition (e.g. PCOS) or use of any medication (e.g., glucocorticoid) deemed by the project physician to interfere with study outcomes.

11a Interventions: description

Participants will be randomized to either low-fat or low-CHO hypocaloric diets for 10wks, followed by a 4-week weight stabilization period, with all food provided throughout.

Energy requirements will be estimated by multiplying REE, measured with indirect calorimetry, by 1.5 (PA factor), and all participants will receive an individualized dietary prescription throughout the weight loss phase (60% of estimated energy needs or 40% energy deficit) and during the 4-week weight stabilization period (energy balance (EB)). During the weight stable phase, diets will be adjusted if weight is not stable. All the food for the duration of Phases 1 and 2 was delivered to the participants' homes on a weekly basis. The low-fat diet was aligned with the USDA guidelines (<http://health.gov/dietaryguidelines/2015/guidelines/>), and was comprised of 55% CHO, 20% fat, and 25% protein. The low-CHO diet was comprised of 25% CHO, 55% fat and 25% protein. Both diets emphasized complex over simple CHO, and allowed dairy products, fruits, and vegetables, within the CHO allowance of each diet.

This will be followed by a 6-month weight maintenance phase with dietary prescription only, where participants will provide their own food. There will be monthly peer group support meetings with the dietitian to discuss nutrition education topics (such as food label reading, portion sizes, tips on eating out, etc). Participants will individually report their body weight to the dietitian and turn in an 8-day food record every month for 6 months.

11b Interventions: modifications

On 06/17/2020, the protocol was amended and approved by UAB IRB to minimize in person contact with participants due to COVID. DXA was replaced with an at home creatine dilution test to measure muscle mass. The post intervention (week 14) IVGTT and Mixed Meal Tolerance tests were omitted from the protocol. The Oral Glucose Tolerance Test at screening was replaced with measurement of Hemoglobin A1c finger stick (choice of at home or in person). Food was delivered to participants home via a commercial provider. The REE and Exercise tests were optional, if participants were not comfortable completing these in-person visits. Participants were given the option to complete the TEE visit at home or in-person. The weekly in-person meetings with the dietitian were moved to a Zoom or phone call and the monthly peer group meetings in Phase 3 were moved to Zoom. Food records were emailed and/or discussed via phone call, with food intake and body weight reported.

11c Interventions: adherance

Strategies used to improve adherence to intervention protocols included weekly phone calls with participants to report previous week's specific food intake, report current body weight, and troubleshooting/support from a Registered Dietitian. Procedures for monitoring adherence include the measurement of respiratory quotient by indirect calorimetry, body weight and composition by bioelectrical Impedance Analysis and blood draw for the quantification of β -hydroxybutyrate, insulin, glucose, triglycerides, and cholesterol.

11d Interventions: concomitant care

Participants will be prohibited from participating in other weight loss programs (diet, exercise, and/or medications that induce weight loss). Participants will be instructed to continue their usual physical activity while in the study.

12. Outcomes

Main outcome measures: S_1 and AIR_g will be measured at baseline with an intravenous glucose tolerance test, body composition with bioimpedance at baseline and Wk10. REE and body composition will also be measured at week 5. REE, TEE, and mechanical efficiency (ME) will be measured with indirect calorimetry, doubly labeled water, and a submaximal bike test, respectively, at baseline and Wk14.

13. Participant timeline

Participants were enrolled between June 2019 and August 2023. Participants will complete 10 weeks of hypocaloric diet, 4 weeks of weight stabilization, and 6 months of weight loss maintenance. See figure 1.

[figure not shown]

Fig. 1 Schematic diagram of the study design.

14. Sample size

This study was powered for differences in FM loss between the two diet groups. Our published data indicate that AA (both men and women) lose more FM when consuming a LG vs HG diet over 16 weeks (1). Subgroup analysis within only the AA women (n=17), for only the 8-week hypocaloric phase, indicated that the women lost more FM with the LG diet [4.5 ± 1.0 (SEM) kg] vs the HG diet [2.0 ± 0.9 (SEM) kg] at a significance level of $P=0.113$. Based on these numbers, with 74 women (37/ group) we would have 80% power to detect a difference of 2.5 kg in FM loss between diets.

15. Recruitment

We will recruit from the local communities (UAB, city of Birmingham, and Jefferson and Shelby counties) via radio, newspaper, web-based advertisement, television advertisement, Research Match, UAB Reporter, word of mouth, and posting of flyers.

Methods: Assignment of interventions

16a Allocation: sequence generation

After baseline testing, participants were randomized to one of two diets (low-glycemic, LG or high glycemic, HG) using a computer generated randomization scheme prepared with PROC PLAN in SAS Ver. 9.4.

16b Allocation concealment mechanism

Randomizations were placed in sealed sequentially numbered envelopes until interventions were assigned. All participants who give consent for participation, who fulfill the inclusion criteria, and complete baseline testing will be randomized. Participants will be enrolled by eligibility from the study team (principal investigator, coordinators, and dietitians). Study Coordinator will open sequentially numbered envelopes for diet intervention. The study dietitians will reveal the diet intervention to participants, along with a detailed diet introduction and explanation.

17a Blinding (masking)

No blinding. Since it was necessary to reveal the diet assignment to the study dietitian and the participant for appropriate diet introduction and education to the participant, this study will not involve blinding.

17b Blinding (masking): emergency unblinding

N/A

Methods: Data collection, management, and analysis

18a Data collection plan

All measurements will be done in the Core facilities of the Center for Clinical and Translational Science (CCTS), Nutrition Obesity Research Center (NORC), and Diabetes Research Center (DRC) at UAB. Participants will be instructed to avoid strenuous physical

activity (PA) the day prior to testing, and all PA on the morning of testing. All S_I tests will be performed in the Clinical Research Unit (CRU) at UAB's CCTS after an overnight fast of 12 h. The following measurements will be performed at baseline and end of weeks 10 and 14, unless otherwise stated.

S_I will be assessed at baseline only using the intravenous glucose tolerance test (IVGTT) and minimal modeling, as previously described (2), but using 300 mg of glucose (20 % dextrose)/kg of body weight. AIRg will be calculated as the incremental insulin area-under-the-curve from minutes 0–10 following glucose injection using the trapezoidal method.

Body composition (FM and fat-free mass) will be determined by bioimpedance analysis (BIA) (Seca 514 mBCA, Seca GmHb & Co. KG, Hamburg, Germany).

Resting Energy Expenditure and substrate utilization will be determined in the CCTS/NORC/DRC Core Laboratory by indirect calorimetry (TrueOne 2400, Parvo Medics, Sandy, UT). Participants will be tested in the fasted (10h) condition following a 30-min supine rest at baseline and week 14.

Total Energy Expenditure will be measured through the CCTS/NORC/DRC Core Laboratory by doubly-labeled water (DLW), at baseline and week 14, using a protocol based on established procedures (3). A FQ of 0.85 will be used at baseline to reflect a standard omnivorous diet, while at week 14, the FQ of the intervention diets will be used (4). FQ will be calculated using the equation of Black et al, $FQ = (CHO\% \times 1.00) + (fat\% \times 0.71) + (protein\% \times 0.81)$ (4).

Mechanical efficiency will be assessed using a submaximal cycling test, in the fasted state, at baseline and week 14. Following a familiarization period, participants cycled at 60 RPM at 10, 20 and 50 watts of power in 4-minute increments. Ventilation, oxygen uptake, carbon dioxide production, respiratory exchange ratio, and heart rate were obtained throughout. Net skeletal muscle work efficiency will be expressed as the ratio of power generated (kcal/min) to the change in EE above REE (kcal/min) at each power output (5).

Laboratory analyses. Blood samples will be collected in the fasting state and concentrations of glucose, β HB, total cholesterol, HDL-cholesterol and triglycerides measured using a SIRRUS analyzer (Stanbio, Boerne, TX), and insulin using a TOSOH A1A-900 immunoassay analyzer (TOSOH Bioscience, South San Francisco, CA) in the CCTS/DRC Core Laboratory. LDL-cholesterol will be calculated using the Friedewald formula (6).

18b Data collection plan: retention

Participant retention will be promoted by weekly communications from the study dietitians and reminder communications from the study coordinators for upcoming in-person testing visits.

19. Data management

Confidentiality will be maintained by coding all data with the subject's identification number. Computerized data will be stored in the Department of Nutrition Sciences database. Paper data will be stored in the Department of Nutrition Sciences in a locked room in a file cabinet. Only qualified research personnel will have access to the database containing the subject information. All subject data that are entered into statistical analyses and publication reports will refer to individuals only by number rather than name.

All records pertaining to medical history, participation in this study, and data collected will be kept strictly confidential and will be recorded only by study number, to protect participant privacy. Only study investigators and the UAB IRB will have access to this data. Information regarding participant demographics, body composition, metabolic outcomes, or blood outcome measures will be shared and labeled with the study number, a unique identifier, and the date of acquisition.

20a Statistics: outcomes

Statistical analysis will be performed with SPSS version 29 (SPSS Inc., Chicago, IL), and data presented as mean \pm SD (or SEM). Statistical significance will be set at $P < 0.05$, unless otherwise specified, and normality of variables was assessed by visual inspection of histogram and Shapiro-Wilk test. Participants will be included in the analysis if they have S_I data at baseline, and body composition at baseline and week 10.

To test the hypothesis that AA women with obesity randomized to a low-CHO diet lose more FM than those randomized to a low-fat diet, we will analyze data from Phase 1 with generalized linear models (GLM). FM at week 10 will be the dependent variable, baseline FM, diet group, and S_I (and/or AIR) the covariates. Finally, to test the hypothesis that S_I (and/or) modulates the response to diet, a “diet \times S_I ” interaction term will be added to the models; i.e., $\Delta FM = \beta_0 + \beta_1 \text{ baseline FM} + \beta_2 \text{ baseline } S_I + \beta_3 \text{ diet group} + \beta_4 \text{ diet group} * S_I + e_1$.

To test the hypothesis that AA women with obesity randomized to a low-CHO diet maintain a higher TEE and REE, and a lower ME, than those randomized to a low-fat diet, we analyzed data from the end of Phase 2 with GLM. TEE, REE, or ME (week 14) were the dependent variables; baseline TEE, REE, or ME, diet group, and S_I (and/or AIRg) the covariates. For all

outcomes, we tested for a phenotype-by-diet interaction by adding relevant interaction terms to the model; e.g., $\Delta\text{TEE} (\text{week 14} - \text{baseline}) = \beta_0 + \beta_1 \text{baseline TEE} + \beta_2 \text{baseline S}_i + \beta_3 \text{diet group} + \beta_4 \text{diet group} * \text{S}_i + e_1$.

We will also test for menopausal status as potential predictors of the independent variables of interest, and include this variable in the models if necessary. The primary analyses will treat S_i as a continuous variable and test for independent and interactive effects of S_i and diet in statistical models. For sub-group analyses the median S_i will be used to designate status: high vs low S_i .

20b Statistics: additional analyses

N/A

20c Statistics: analysis population and missing data

N/A

Methods: Monitoring

21a Data monitoring: formal committee

[name] –Professor in the Department of Nutrition Sciences is appointed as the Independent Safety Monitor to provide independent monitoring and review of the protocol every 6 months.

21b Data monitoring: interim analysis

Description of interim analyses and stopping guidelines:

22. Harms

If an individual indicates discomfort or the desire to discontinue testing, tests will be terminated immediately. During routine visits and telephone calls, the study coordinator will query

participants for any adverse events since their last contact with study personnel. In the case of an adverse event during times of testing, a study physician will be on call. The physician will provide medical supervision for this study. All adverse events will be reported to the UAB IRB and reviewed by the investigative team. Should any of these individuals and/or the IRB identify that any adverse event may be related to the study protocol, testing will be suspended, and the protocol will be amended accordingly.

23. Auditing

A progress report will be submitted annually to the sponsor and to UAB IRB.

Ethics and dissemination

24. Research ethics approval

The study is approved by UAB IRB (IRB-300001324) and annual progress reports will be sent to UAB IRB during the full duration of the study.

25. Protocol amendments

On 06/17/2020, the protocol was amended and approved by UAB IRB to minimize in person contact with participants due to COVID. DXA was replaced with an at home creatine dilution test to measure muscle mass. The post intervention (week 14) IVGTT and Mixed Meal Tolerance tests were omitted from the protocol. The Oral Glucose Tolerance Test at screening was replaced with measurement of Hemoglobin A1c finger stick (choice of at home or in person). Food was delivered to participants home via a commercial provider. The REE and Exercise tests were optional, if participants were not comfortable completing these in-person visits. Participants were given the option to complete the TEE visit at home or in-person. The weekly in-person meetings with the dietitian were moved to a Zoom or phone call and the

monthly peer group meetings in Phase 3 were moved to Zoom. Food records were emailed and/or discussed via phone call, with food intake and body weight reported.

26a Consent

The study coordinator will obtain informed consent from trial participants. Potential participants who met the inclusion criteria for the study will be asked to review the consent form and if interested, to contact Study Coordinators. If an individual is eligible to join the study, a screening measurement will be scheduled. During this visit, the project coordinator will review the consent form and obtain informed consent. The consenting process is confidential, and will take place in a private room.

26b Consent: ancillary studies

N/A

27. Confidentiality

Confidentiality is maintained by coding all data with the subject's identification number. Computerized data will be stored in the Department of Nutrition Sciences database. Paper data will be stored in the Department of Nutrition Sciences in a locked room in a file cabinet. Only qualified research personnel have access to the database containing the subject information. All subject data that are entered into statistical analyses and publication reports will refer to individuals only by number rather than name.

All records pertaining to medical history, participation in this study, and data collected will be kept strictly confidential and will be recorded only by study number, to protect participant privacy. Only study investigators and the UAB IRB will have access to this data. Information regarding participant demographics, body composition, metabolic outcomes, or blood outcome

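### The week-10 fat-mass model leaves out the baseline energy gap, which the trial can estimate from its own pre-randomization TEE: a loss of precision for diet, and an untested activity explanation for the S_I and AIRg main effects

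*Combined protocol and SAP*

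**What the plan says.** - **Prescription (11a).** "Energy requirements will be estimated by multiplying REE, measured with indirect calorimetry, by 1.5 (PA factor". The weight-loss diet then supplies "60% of estimated energy needs or 40% energy deficit". One factor applies to everyone.
- **Adjustment (11a).** "During the weight stable phase, diets will be adjusted if weight is not stable". This concerns the four weeks after week 10. Nothing comparable is stated for the ten hypocaloric weeks over which FM loss is judged.
- **Who is enrolled (10, 11d).** Eligible women are "Sedentary to moderately active", with no numeric limits. "Participants will be instructed to continue their usual physical activity while in the study".
- **What is measured (18a, 16a).** TEE is obtained "by doubly-labeled water (DLW), at baseline and week 14", and randomization follows baseline testing, so baseline TEE is a pre-randomization variable.
- **The model (20a).** "FM at week 10 will be the dependent variable, baseline FM, diet group, and" S_I and/or AIRg are the covariates, with diet × S_I added for the modulation hypothesis. Baseline TEE appears only in the model for week-14 TEE.
- **The hypothesis (1.1, 2.1).** Section 1.1 expects the FM effect to be modulated by energy expenditure. Section 2.1 asks for independent as well as interactive effects of S_I, AIRg and diet. No FM model contains an expenditure term.

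**The concern.** Fat loss is driven by expenditure minus intake. Here intake is tied to REE alone, while expenditure also depends on activity, which differs between women and is meant to stay as it was. Two women with the same REE receive the same energy but can face quite different deficits. That predictable variation goes into the residual of the FM model.

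Two things are at stake. For the diet and diet × S_I tests it is precision. For the S_I and AIRg main effects it is interpretation. These phenotypes are not randomized, and if more active women are also more insulin sensitive, their coefficients can carry part of an activity effect.

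**Working it through.** **1. The stated deficit.** Intake = 0.60 × 1.5 × REE = 0.90 × REE. Deficit = 1 − 0.90/(TEE/REE). At 1.5 this gives 40%, the plan's figure. The documents give no TEE/REE range. For assumed values of 1.3, 1.4, 1.6, 1.7 and 1.8 the deficit is 30.8%, 35.7%, 43.8%, 47.1% and 50.0%.

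**2. In kilograms.** Assumptions, none from the documents: REE 1,600 kcal/day, SD of TEE/REE 0.10–0.15, 9,400 kcal per kg of fat, 70 days. SD of potential FM loss due to activity:
- 0.10 × 1,600 × 70 / 9,400 = 1.19 kg
- 0.15 × 1,600 × 70 / 9,400 = 1.79 kg

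These are upper bounds. They assume full adherence, no metabolic adaptation, all energy lost as fat, error-free TEE, and no overlap with baseline FM or S_I.

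**3. Precision of the diet test.** Section 14 states 80% power for 2.5 kg with 37 per group. At two-sided 5% (sidedness is not stated) that implies an SD of 3.79 kg by the t-distribution, or 3.84 kg by the normal approximation. The pilot SEMs in the same section (1.0 and 0.9 kg, 17 women, split not given) imply 2.76–2.99 kg over splits from 6/11 to 11/6, and power of 94–97% at 37 per group. That mismatch is a separate matter; here it means showing both SDs.

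| SD | Variance removed | Residual SD | Power |
|---|---|---|---|
| 3.79 kg | none | 3.79 | 80% |
| 3.79 kg | 1.19²/3.79² = 10% | 3.60 | 84% |
| 3.79 kg | 1.79²/3.79² = 22% | 3.34 | 89% |
| 2.9 kg | none | 2.9 | about 96% |
| 2.9 kg | 10% | 2.75 | 97% |
| 2.9 kg | 25% | 2.51 | 99% |

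At 2.9 kg the kilogram figures in step 2 would be 17–38% of variance (1.19²/2.9², 1.79²/2.9²), giving 98% to just over 99%. There is little room to gain there.

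**4. The S_I main effect.** If S_I and TEE/REE correlate at r, the S_I coefficient absorbs r × (activity SD) per SD of S_I. With r assumed at 0.2–0.3:
- Bias: 0.2 × 1.19 = 0.24 kg to 0.3 × 1.79 = 0.54 kg per SD.
- Standard error at SD 3.79: 3.79/√74 = 0.44 kg, so the bias is 0.5–1.2 standard errors and the false-positive rate about 8–23% instead of 5%.
- At SD 2.9: standard error 0.34 kg, false-positive rate about 11–36%.

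Each range pairs the low inputs together and the high inputs together. At r = 0 there is no bias.

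**5. Simulation.** 74 women, 4,000 runs, no true diet or S_I effect, SD of TEE/REE 0.15, total SD 3.84 kg, activity term omitted:

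| r | Diet rejection | Diet × S_I rejection | S_I bias (kg/SD) | S_I rejection |
|---|---|---|---|---|
| 0 | 4.4% | 5.2% | about 0 | 5% |
| 0.2 | 4.8% | 4.7% | 0.35 | 12% |
| 0.4 | 4.8% | 5.0% | 0.71 | 35% |

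Diet and diet × S_I bias were about zero throughout. Adding TEE/REE returned the S_I rejection rate to about 5%.

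**The case against.** The strongest reply is that nothing randomized is wrong. Activity is balanced between arms in expectation, and chance imbalance is already in the standard error. Leaving out a prognostic covariate is a choice about efficiency, and at the pilot SD power is high without it. All of this stands. A reader might infer that the single 1.5 factor biases the diet comparison; the simulation shows it does not. Diet × S_I would be distorted only if the effect of activity itself differed by diet.

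Second, the S_I bias rests on a correlation that the documents do not give and that would have to persist after conditioning on baseline FM. This also stands: the figures show what could happen, not what has happened. "Independent" in section 2.1 may mean no more than a main effect beside an interaction, so the plan does not claim an S_I effect free of activity.

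Third, adjustment could remove what is being studied. Section 1.1 treats expenditure as part of the hypothesis, and the introduction links insulin action to whether food is stored or burned. If S_I acts partly through expenditure, adjusting for baseline TEE changes what its coefficient means. This is a good reason not to let an adjusted S_I estimate replace the unadjusted one, but no reason to leave the question unexamined.

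Finally, baseline TEE might be taken to measure the true gap. It does not: that needs actual intake and expenditure during the diet. It estimates the starting gap only.

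**Conclusion.** The point holds as a recommended improvement to section 20a. The FM model omits a baseline variable that the trial schedules, that bears directly on the outcome, and that the trial's own hypothesis names.

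- **Diet and diet × S_I:** unbiased, with some precision lost. For the diet test the gain is at most from 80% to about 84–89% if the SD is near 3.8 kg, and from about 96% to 97–99% if it is near 2.9 kg. The documents do not support reading this as a flaw that undermines the randomized result.
- **S_I and AIRg main effects:** open to an activity explanation of unknown size. With assumed correlations of 0.2–0.3 the S_I bias is about 0.24–0.54 kg per SD, with a false-positive rate of about 8–23% at SD 3.8 kg. The same reasoning applies to AIRg if it correlates with activity. The documents do not show that such confounding is present.

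The size rests on assumed REE, spread of TEE/REE, energy density and correlation. That the prescription is fixed relative to REE and the expenditure term is missing rests on the text alone.

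**What to change.** Leave the diets as they are and change section 20a:

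1. Prespecify one covariate, baseline doubly-labeled-water TEE minus the issued Phase 1 energy prescription (kcal/day), in the week-10 FM models used for the diet and diet × S_I tests. Name this form only. It equals REE × (TEE/REE − 0.9), so it also carries body size and is not interchangeable with TEE/REE; with assumed REE SD 200 kcal/day and TEE/REE mean 1.5, SD 0.125, the two correlate at about 0.85.
2. Impute missing baseline values from baseline data only, blind to arm, so that no woman is dropped. Section 20c has no missing-data rule, and the 2020 amendment in 11b made the REE test optional. Using the issued prescription means the covariate needs TEE and the prescription record, not a separate REE value.
3. Report the S_I and AIRg main effects both without and with the covariate, and state that the two estimates answer different questions.
4. If analysis has already begun, label the adjusted results a sensitivity analysis.

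The cost is SAP wording, one degree of freedom, an imputation rule, and a second estimate of each phenotype effect to interpret. No visit or measurement is added.

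### The printed low-CHO diet adds to 105%; entered in the planned FQ equation, it would understate week-14 TEE in that arm by about 3.4% to 4.9%

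*Combined protocol and SAP*

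**What the plan says.** Section 11a defines the two diets. The low-fat diet "was comprised of 55% CHO, 20% fat, and 25% protein", which adds to 100%. For the other arm it says: "The low-CHO diet was comprised of 25% CHO, 55% fat and 25% protein". No other section gives a macronutrient split for the low-CHO diet.

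Section 18a measures TEE by doubly labeled water at baseline and week 14. The FQ differs by visit. One fixed value serves both arms at the first visit: "A FQ of 0.85 will be used at baseline to reflect a standard omnivorous diet". For the later visit the section switches to diet-specific values: "while at week 14, the FQ of the intervention diets will be used". The diet FQ is a weighted sum of the diet's carbohydrate, fat and protein percentages, with weights 1.00, 0.71 and 0.81. The section gives no numerical FQ for either diet, does not say whether the percentages come from 11a or from the menus, and does not name the equation that converts CO2 production to energy.

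TEE is among the secondary objectives in section 2.2: "To characterize REE, TEE, and ME following low-CHO, versus low-fat diet". Section 20a attaches a directional hypothesis, that women on low-CHO "maintain a higher TEE and REE, and a lower ME, than those randomized to a low-fat diet". It is tested with week-14 TEE as the dependent variable, adjusted for baseline TEE.

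**The concern.** The FQ equation is a weighted average only when the three fractions sum to 1. With a total of 1.05, the surplus adds directly to the FQ, and too high an FQ makes the TEE derived from a given CO2 production too low.

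Two things are at stake. First, the composition defines one of the two randomized interventions, and as printed that diet cannot be reproduced: it could be 20/55/25, 25/50/25, 25/55/20 or something else. Second, if the printed figures were used, week-14 TEE would be too low in the low-CHO arm only. Baseline uses 0.85 for everyone, and the low-fat figures already sum to 100%. Neither randomization nor baseline adjustment removes a conversion error confined to one arm at follow-up. It would pass into the diet coefficient for TEE and count against the stated hypothesis.

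**Working it through.** **Inputs from the document.** Low-CHO 25/55/25 and low-fat 55/20/25, as CHO/fat/protein (11a). FQ = 1.00 × CHO + 0.71 × fat + 0.81 × protein, and baseline FQ 0.85 (18a).

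**Assumptions not in the document.** A Weir-type conversion, TEE = VCO2 × k with k = 1.106 + 3.941/FQ, and a true TEE of 2000 to 2800 kcal/d. The plan has no FQ or TEE figure of its own to reproduce.

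**Step 1: sums.** Low-fat: 55 + 20 + 25 = 100. Low-CHO: 25 + 55 + 25 = 105.

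**Step 2: FQ from the printed figures.**
- Low-fat: 0.55 + 0.20 × 0.71 + 0.25 × 0.81 = 0.8945
- Low-CHO: 0.25 + 0.55 × 0.71 + 0.25 × 0.81 = 0.25 + 0.3905 + 0.2025 = 0.843

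**Step 3: low-CHO compositions that sum to 100%.** Each keeps two printed figures and lowers the third by 5 points, or divides all three by 1.05. The understatement is 1 − 5.781/k, where 5.781 = 1.106 + 3.941/0.843.

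| CHO/fat/protein | FQ | k | TEE understated by | at 2000 kcal/d | at 2800 kcal/d |
|---|---|---|---|---|---|
| 25/50/25 | 0.8075 | 5.987 | 3.43% | 69 | 96 |
| rescaled by 1/1.05 | 0.8029 | 6.015 | 3.89% | 78 | 109 |
| 25/55/20 | 0.8025 | 6.017 | 3.92% | 78 | 110 |
| 20/55/25 | 0.7930 | 6.076 | 4.85% | 97 | 136 |

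Other coefficient pairs in the conversion (3.9 and 1.1; 3.9 and 1.11; 3.815 and 1.232) give 3.3% to 4.9%, so the result depends little on the exact equation.

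**Step 4: effect on change from baseline.** At baseline, k = 1.106 + 3.941/0.85 = 5.742. With CO2 production unchanged, the switch of FQ alone moves converted TEE by:
- low-CHO as printed: 5.781/5.742 − 1 = +0.7%
- low-CHO summing to 100%: +4.2% (25/50/25) to +5.8% (20/55/25)
- low-fat: 5.512/5.742 − 1 = −4.0%

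Using 0.843 would therefore remove most of the adjustment that the diet-specific FQ is meant to make in the low-CHO arm.

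**Step 5: what diet has an FQ of 0.843?** With protein at 25%, solve c + 0.71 × (0.75 − c) + 0.2025 = 0.843. Then 0.29c = 0.108, so c = 0.372: about 37% CHO and 38% fat, far from the printed 25% and 55%.

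**The case against.** The strongest reply is that this may be a typing slip with no effect on any data. All food was supplied in Phases 1 and 2, so menus existed. Section 18a refers to the FQ of the diets and does not say that the rounded figures in 11a are the input. Energy fractions from a real menu sum to 1 and need no rescaling. This stands: the TEE error is conditional, and it is zero if menus were used. But the document does not show which source was used, and 11a holds the only percentages it offers for the equation.

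The figures may also be rounded. Every printed percentage is a multiple of 5, and a diet of 23.3/53.3/23.4 sums to 100 and rounds to 25/55/25. That would make the line loose reporting instead of an error in one component. It does not make the figures safe to enter: that diet has FQ = 0.233 + 0.533 × 0.71 + 0.234 × 0.81 = 0.801, inside the range above.

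Three further limits are fair. The conversion equation and the TEE level are assumptions. The 3.4% to 4.9% range covers one component 5 points too high or all three proportionally high; errors in several components could fall outside it. And the low-fat FQ of 0.8945 is only consistent with printed figures that sum to 100%. The delivered low-fat composition is not shown either, so confining the error to one arm rests on the printed figures.

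Finally, eligibility, randomization, the sample size and the primary fat-mass model do not use FQ. That is correct and limits the consequence to TEE and the description of the intervention.

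**Conclusion.** The concern holds and should be fixed. That the low-CHO composition adds to 105% is certain and needs no assumption, and the document gives no means of resolving it. The consequence for TEE is conditional: followed with the printed figures, the plan gives the low-CHO arm too high an FQ and too low a week-14 TEE, by the 3.4% to 4.9% derived above. That size rests on the assumed Weir-type conversion and on the one-component or proportional form of the error. It is not shown that any TEE value is wrong. The point is more than clerical, because the figure both defines a randomized diet and is a natural input to a secondary outcome with its own hypothesis.

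**What to change.** 1. In 11a, correct the low-CHO composition from the delivered menus so that it adds to 100%. Which figure is wrong is for the sponsor to establish.
2. In 18a, state that week-14 FQ is computed from energy fractions required to sum to 1, and give the FQ value used for each arm.
3. If 0.843 was used, recalculate week-14 TEE in the low-CHO arm and rerun the TEE models.

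The cost is one corrected line, one added sentence and, only in the third case, a recalculation from existing measurements. No new data are needed.
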